8.2 Statistical Hypotheses

656 The primary objective of the study is assessment of safety. Therefore, there are no formal statistical
657 hypotheses associated with any of the endpoints. Outcomes will be primary descriptive in nature.

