Number of Participants	Up to 20 participants signing consent to use the study devices, with a goal that at least 10 complete the study.
Participant Population:	
Eligibility to enroll in the study will be assessed based on the following inclusion criteria:
 
 1. Age \geq18 years old 2. Diagnosis of type 1 diabetes for at least 1 year 3. Current Control-IQ user, having been prescribed Control-IQ for at least 3 months 4. HbA1c \leq 10%, recorded in the last 3 months 5. Investigator has confidence that the participant can successfully operate all study devices and is capable of adhering to the protocol, including performing the weekend hotel observed setting portion of the study. 6. Willing to use only aspart (novorapid) or lispro (humalog) insulin with the study pump, with no use of long-acting basal insulin injections, or inhaled insulin with the study pump. 7. Have current glucagon product to treat severe hypoglycemia (injectable or nasal) at home (site will provide prescription if they do not have one) 
Eligibility to enroll in the study will be assessed based on the following exclusion criteria:
 
 1. More than 1 episode of diabetic ketoacidosis (DKA) in the past 6 months 2. More than 1 episode of severe hypoglycemia (needing assistance) in the past 6 months 3. Inpatient psychiatric treatment in the past 6 months 4. For Female: Currently pregnant or planning to become pregnant during the time period of study participation 
 a. A negative pregnancy test will be required for all females of child-bearing potential b. Counseling on appropriate birth control options will be provided to all females of child-bearing potential 5. Concurrent use of any non-insulin glucose-lowering agent, other than metformin (for example, GLP-1 agonists, Symlin, DPP-4 inhibitors, SGLT-2 inhibitors, sulfonylureas). 6. Hemophilia or any other bleeding disorder 7. Hemoglobinopathy

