8.1 General Statistical Considerations

649 Summary statistics will be generated for all relevant variables. In the comparison of continuous variables,
650 distributions will be tested for the normality assumption. If standard parametric techniques are found to be
651 inadequate, an appropriate non-parametric technique will be used. Categorical variables will be presented
652 using frequencies and percentages and compared using differences in proportions unless stated otherwise.
653 For safety/adverse event reporting, both the number of overall events and the number of participants
654 experiencing that event will be tabulated. No corrections will be made for multiple testing procedures.

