8.3 Sample Size

659 The sample size of at least 10 participants completing the trial is required. As this is a feasibility study
660 assessing safety, this sample size is for a convenience sample and is not based on a power analysis.

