8.4 Outcome Measures

662 The two study periods are:

663 1) Control-IQ at home run-in period.
664 2) The Tandem Freedom hotel observed weekend period.

Primary Endpoints for each period:

666 1. Severe hypoglycemia (with cognitive impairment such that assistance of another individual is needed
667 for treatment)

668 2. Number of diabetic ketoacidosis events

669 3. Number of unanticipated adverse device effects

670 4. Number of other serious device-related adverse events

671 Secondary Endpoints for each period:

672 1. All device-related adverse events

673 2. CGM hypoglycemia outcomes

674 a. Overall % time <3.0 mmol/L

675 b. Overall % time <3.9 mmol/L

676 3. Times in ranges-overall (3.9-10 mmol/L, >10 mmol/L, >13.9 mmol/L, 3.9-7.9 mmol/L)

677 4. Mean glucose

678 5. Overall variability (CV and SD)

679 6. Secondary endpoints 2 - 5 daytime and nighttime

680 Due to the small sample size and feasibility nature of the study, primarily descriptive statistics will be
681 used.

682 **8.5 Baseline Descriptive Statistics**

683 Baseline demographic and clinical characteristics of the cohort of participants will be summarized in a
684 table using summary statistics appropriate to the distribution of each variable. Descriptive statistics will
685 be displayed by treatment group for the following:

686 • Age
687 • Sex
688 • Ethnicity
689 • Socio-economic factors (household income, education)
690 • Diabetes duration
691 • HbA1c
692 • Body Mass Index
693 • Total daily insulin
694 • Prior severe hypoglycemia and DKA events in the last 6 months

695 **8.6 Additional Tabulations and Analyses**

696 The following data will be tabulated at baseline, for the run-in period, and for the hotel supervised period

697 • Insulin metrics (units/kg): total daily insulin, total daily manual insulin.

698 **8.7 Device Issues**

699 The following tabulations will be performed with respect to device issues:

700 • Number of device issues by type, and number of unique participants with each type of device issue

701 **8.8 Multiple Comparison/Multiplicity**

702 There are no adjustments performed for multiple comparisons.

703 **8.9 Handling of Missing Data**

704 All practical monitoring and follow-up steps will be taken to ensure complete and accurate data
705 collection. All analyses will be based on available data only; no imputation for missing data is planned.

706

707 **Chapter 9: Data Collection and Monitoring**

708 **9.1 Case Report Forms and Other Data Collection**

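### The four primary safety endpoints are planned without any measure of precision, although a zero count would leave a two-sided 95% upper limit of 30.8% with 10 participants and 16.8% with 20

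*Combined protocol and SAP*

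**What the plan says.** Section 8.2 states: "The primary objective of the study is assessment of safety". It continues "Therefore, there are no formal statistical" hypotheses for any endpoint, and adds "Outcomes will be primary descriptive in nature".

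Section 8.4 lists four primary endpoints for each of two periods, the Control-IQ run-in at home and the Tandem Freedom hotel weekend. They are severe hypoglycemia, DKA, unanticipated adverse device effects and other serious device-related adverse events. They are framed as numbers of events, for example "Number of diabetic ketoacidosis events".

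Section 8.1 sets the tabulation rule: "For safety/adverse event reporting, both the number of overall events and the number of participants" with the event are to be shown. Categorical variables are given as frequencies and percentages. Neither section names a confidence interval, and none appears elsewhere in the document.

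On size, Section 8.3 says "The sample size of at least 10 participants completing the trial is required" and explains that, for a feasibility study "assessing safety, this sample size is for a convenience sample and is not based on a power analysis". The Protocol Summary gives the ceiling: "Up to 20 participants signing consent to use the study devices, with a goal that at least 10 complete the study".

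**The concern.** The primary result of the study will be a short table of small counts. A count, a number of participants and a percentage do not show how much risk the data leave open, and this matters most when the count is zero: 0 (0%) looks the same from 10 participants as from 1,000.

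Having no hypothesis explains why there is no test and no power calculation. It does not explain the lack of a precision statement, because an interval is itself a descriptive summary. The result will also be used outside the study. Section 6.5 says that the Medical Monitor's final classification determines the safety endpoints and serves regulatory reports, labeling and publications. Readers of those documents need to know what the count can exclude.

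**Working it through.** **The plan's own figure.** The only figure is the minimum of 10 completers (Section 8.3). It has no stated event rate, precision target or power, so there is no calculation to reproduce.

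**Inputs.**
- Number of participants: at least 10 completers (8.3) and up to 20 consenting (Protocol Summary). Starters of a period cannot be fewer than its completers, so if the target is met, the number starting Tandem Freedom lies between 10 and 20. The value of 12 below is an illustration.
- Confidence level: not stated. Two-sided 95% is assumed, with one-sided 95% as a variant.
- Event rate: not stated. A range of true risks is shown.
- Exposure: 7 ± 3 days of run-in (3.1). Tandem Freedom use runs from the evening of Day 1 to the morning of Day 4 (Protocol Summary; 3.2.2, 3.2.5), about 2.5 days.

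**Step 1: upper limit after zero events.** The exact (Clopper-Pearson) limit solves (1 − p)^n = α/2 two-sided, or α one-sided. Hence p = 1 − 0.025^(1/n) or p = 1 − 0.05^(1/n).

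| Participants, n | Two-sided 95% | One-sided 95% |
|---|---|---|
| 10 | 30.8% | 25.9% |
| 12 | 26.5% | 22.1% |
| 15 | 21.8% | 18.1% |
| 20 | 16.8% | 13.9% |

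Check at n = 10: with p = 0.3085, (1 − 0.3085)^10 = 0.025. Other methods agree in scale at n = 10: the rule of three gives 3/10 = 30% and the Wilson limit is 27.8%.

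**Step 2: one event.** For 1 of 10 the exact two-sided 95% interval is 0.3% to 44.5%, so the imprecision is not peculiar to zero.

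**Step 3: how often a clean table arises.** The chance of no event in n participants is (1 − p)^n.

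| Assumed true risk per participant | n = 10 | n = 20 |
|---|---|---|
| 1% | 90% | 82% |
| 5% | 60% | 36% |
| 10% | 35% | 12% |

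A clean table with 10 participants is thus quite compatible with a true risk of 5% or 10%.

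**Step 4: why the two periods' intervals are not a comparison.** Zero events in 10 participants gives the same 30.8% in both periods, but the exposures differ: 10 × 2.5 = 25 participant-days on Tandem Freedom, against 10 × 7 = 70 in the run-in (40 to 100 over the permitted 4 to 10 days). On a rate scale the two-sided limit is −ln(0.025) = 3.689 divided by exposure: 3.689/25 = 0.148 per participant-day against 3.689/70 = 0.053. The hotel period is also supervised around the clock and the run-in is not.

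**The case against.** The strongest reply is that the plan claims nothing an interval would correct. It has no success criterion and no rule for declaring safety. It says openly that the sample is one of convenience and that small numbers are the reason for descriptive statistics. The counts are not bare either, since participants with events and percentages are planned, and anyone given n can work out the limit. Safety is also judged on more than these counts: Section 8.4 has all device-related adverse events and CGM time in hypoglycemia as secondary endpoints, and Section 6.6.1 provides for review of every severe hypoglycemia or DKA event.

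Much of this stands, and it limits the point in four ways.
- A reader might infer that zero events will be presented as proof of safety. The documents do not support that: no safety claim is prespecified, and how a report would word its conclusion is not known. Nor is there a basis for dictating that wording here.
- A reader might take 31% as the figure for this trial. It holds only at the minimum of 10 and at a two-sided 95% level that the plan does not state.
- That zero is the likely result is plausible for about 2.5 supervised days, but it remains an assumption.
- A reader might infer that the sample size is wrong. For a feasibility study with no hypothesis, nothing in the documents shows that.

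What the reply does not answer is the gap itself. Small numbers are acknowledged but never quantified, and leaving readers to derive the limit is weaker than stating it for a primary endpoint.

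**Conclusion.** The point holds as a reporting gap of modest weight that should be closed. Safety is the primary objective, and no primary safety endpoint carries a measure of precision. If no events are seen, the data would remain compatible with a per-participant risk of up to 30.8% with 10 participants or 16.8% with 20 (two-sided 95%); one-sided, 25.9% and 13.9%. The arithmetic is exact. The confidence level and the zero count are assumptions, and the per-participant scale takes no account of exposure time.

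**What to change.** In Sections 8.1 and 8.4, for each primary endpoint and each period, add the proportion of participants with at least one event and its exact (Clopper-Pearson) two-sided 95% interval. Use as denominator the participants who started that period; for the second period, those who started Tandem Freedom. Starters fit Section 7.7, which keeps data up to withdrawal, and avoid one denominator in the table and another in the sample size text.

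Show each period's exposure time next to the interval, and say that the two intervals are not to be read as a comparison.

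In Section 8.3, state what a zero count would leave open on the same denominator, as a range: 30.8% for 10 starters, 26.5% for 12 and 16.8% for 20.

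The sample size does not change, and no further data or participants are needed. The cost is a few sentences in Chapter 8, one more table column with the exposure time beside it, and a safety result that looks less favourable.

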8.3 Sample Size

659 The sample size of at least 10 participants completing the trial is required. As this is a feasibility study
660 assessing safety, this sample size is for a convenience sample and is not based on a power analysis.

8.4 Outcome Measures

662 The two study periods are:

663 1) Control-IQ at home run-in period.
664 2) The Tandem Freedom hotel observed weekend period.

Primary Endpoints for each period:

666 1. Severe hypoglycemia (with cognitive impairment such that assistance of another individual is needed
667 for treatment)

668 2. Number of diabetic ketoacidosis events

669 3. Number of unanticipated adverse device effects

670 4. Number of other serious device-related adverse events

671 Secondary Endpoints for each period:

672 1. All device-related adverse events

673 2. CGM hypoglycemia outcomes

674 a. Overall % time <3.0 mmol/L

675 b. Overall % time <3.9 mmol/L

676 3. Times in ranges-overall (3.9-10 mmol/L, >10 mmol/L, >13.9 mmol/L, 3.9-7.9 mmol/L)

677 4. Mean glucose

678 5. Overall variability (CV and SD)

679 6. Secondary endpoints 2 - 5 daytime and nighttime

680 Due to the small sample size and feasibility nature of the study, primarily descriptive statistics will be
681 used.

682 **8.5 Baseline Descriptive Statistics**

683 Baseline demographic and clinical characteristics of the cohort of participants will be summarized in a
684 table using summary statistics appropriate to the distribution of each variable. Descriptive statistics will
685 be displayed by treatment group for the following:

686 • Age
687 • Sex
688 • Ethnicity
689 • Socio-economic factors (household income, education)
690 • Diabetes duration
691 • HbA1c
692 • Body Mass Index
693 • Total daily insulin
694 • Prior severe hypoglycemia and DKA events in the last 6 months

695 **8.6 Additional Tabulations and Analyses**

696 The following data will be tabulated at baseline, for the run-in period, and for the hotel supervised period

697 • Insulin metrics (units/kg): total daily insulin, total daily manual insulin.

698 **8.7 Device Issues**

699 The following tabulations will be performed with respect to device issues:

700 • Number of device issues by type, and number of unique participants with each type of device issue

701 **8.8 Multiple Comparison/Multiplicity**

702 There are no adjustments performed for multiple comparisons.

703 **8.9 Handling of Missing Data**

704 All practical monitoring and follow-up steps will be taken to ensure complete and accurate data
705 collection. All analyses will be based on available data only; no imputation for missing data is planned.

706

707 **Chapter 9: Data Collection and Monitoring**

708 **9.1 Case Report Forms and Other Data Collection**

709 The main study data are collected on electronic case report forms (eCRFs). Original source
710 documentation will be maintained in the participant's study chart or medical record. This source must be
711 readily verifiable against the values entered into eCRF.

712 Electronic device data files are obtained from the study software and individual hardware components.
713 These electronic device files are considered the primary source documentation.

714 **9.2 Study Records Retention**

715 Each participating site will maintain appropriate medical and research records for this trial, in
716 compliance with GCP and regulatory and institutional requirements for the protection of confidentiality of
717 participants.

718 Study documents should be retained for a minimum of 10 years after the last approval of a marketing
719 application in an ICH region and until there are no pending or contemplated marketing applications in an
720 ICH region or until at least 2 years have elapsed since the formal discontinuation of clinical development
721 of the investigational product. These documents should be retained for a longer period, however,
722 if required by local regulations. No records will be destroyed without the written consent of the sponsor,
723 if applicable. It is the responsibility of the sponsor to inform the investigator when these documents no
724 longer need to be retained.

725 **9.3 Quality Assurance and Monitoring**

726 Designated personnel from the Coordinating Center will be responsible for maintaining quality
727 assurance (QA) and QC systems to ensure that the clinical portion of the trial is conducted and data are
728 generated, documented and reported in compliance with the protocol, GCP and the applicable regulatory
729 requirements, as well as to ensure that the rights and wellbeing of trial participants are protected and that
730 the reported trial data are accurate, complete, and verifiable. Adverse events will be prioritized for
731 monitoring.

732 A monitoring plan will be developed and revised as needed during the course of the study. Study conduct
733 and monitoring will conform with 21 Code of Federal Regulations (CFR) 812 and Guideline on the
734 Regulation of Therapeutic Products in New Zealand Part 11: Clinical trials – regulatory approval and
735 good clinical practice requirements, including the Guideline for Good Clinical Practice E6(R2)
736 (EMA/CHMP/ICH/135/1995). This plan will describe in detail who will conduct the monitoring, at what
737 frequency monitoring will be done, at what level of detail monitoring will be performed, and the
738 distribution of monitoring reports.

739 A data management plan will be also be developed and revised as needed during the course of the study.

740 The data of most importance for monitoring at the site are participant eligibility and adverse events.
741 Therefore, the monitoring plan will focus on these areas. As much as possible, remote monitoring will be
742 performed in real-time with on-site monitoring performed to evaluate the verity and completeness of
743 the key site data. Elements of the monitoring may include:

744 • Qualification assessment, training, and certification for sites and site personnel
745 • Oversight of HDEC coverage and informed consent procedures
746 • On-site monitoring (site visit): source data verification, data edits/audit trail, protocol review of
747 entered data and edits, statistical monitoring, study closeout, site visit report
748 • Agent/Device accountability
749 • Communications with site staff
750 • Patient retention and visit completion
751 • Management of noncompliance
752 • Documenting monitoring activities
753 • Adverse event reporting and monitoring

754 Sponsor representatives or their designees may visit the study facilities at any time in order to maintain
755 current and personal knowledge of the study through review of the records, comparison with source
756 documents, observation and discussion of the conduct and progress of the study. The investigational site
757 will provide direct access to all trial related source data/documents, and reports for the purpose of
758 monitoring and auditing by the sponsor, and inspection by local and regulatory authorities.

759 **9.4 Protocol Deviations**

760 A protocol deviation is any noncompliance with the clinical trial protocol, GCP, or procedure
761 requirements. The noncompliance may be either on the part of the participant, the investigator, or the
762 study site staff. A significant (or major) deviation is any deviation that departs from the established
763 materials in such a way that it poses an increase in the risk to participants, adversely affects the welfare,
764 rights, or safety of the research participants, or negatively influences the scientific study integrity. As a
765 result of a significant deviation, a corrective and preventive action plan shall be developed by the site
766 and implemented promptly.

767 The site PI/study staff is responsible for knowing and adhering to HDEC requirements. Further details
768 about the handling of protocol deviations will be included in the monitoring plan.

769

770

Chapter 10: Ethics/Protection of Human Participants

771

10.1 Ethical Standard

772

The investigator agrees that the study will be conducted according to the applicable New Zealand regulations (Medsafe and Health and Disability Ethics Committee), International Conference on Harmonization (ICH) guidelines on Good Clinical Practice (GCP) and the principles of the World Medical Association Declaration of Helsinki 2008. The investigator will conduct all aspects of this study in accordance with all national, state, and local laws or regulations.

777

10.2 Institutional Review Boards

778

The protocol, informed consent form(s), recruitment materials, and all participant materials will be submitted to the Health and Disability Ethics Committee (HDEC) for review and approval. Full HDEC approval must be obtained before any participant is enrolled. Only substantial amendments to the protocol will require HDEC review and approval before the changes are implemented to the study. All substantial changes to the consent form will be HDEC approved.

783

10.3 Informed Consent Process

784

10.3.1 Consent Procedures and Documentation

785

Informed consent is a process that is initiated prior to the individual's agreeing to participate in the study and continues throughout the individual's study participation. Extensive discussion of risks and possible benefits of participation will be provided to the participants and their families. Consent forms will be HDEC-approved and the participant will be asked to read and review the document. The investigator will explain the research study to the participant and answer any questions that may arise. All participants will receive a verbal explanation in terms suited to their comprehension of the purposes, procedures, and potential risks of the study and of their rights as research participants. Participants will have the opportunity to carefully review the written consent form and ask questions prior to signing.

793

The participants should have the opportunity to discuss the study with their surrogates or think about it prior to agreeing to participate. The participant will sign the informed consent document prior to any procedures being done specifically for the study. The participants may withdraw consent at any time throughout the course of the trial. A copy of the informed consent document will be given to the participants for their records. The rights and welfare of the participants will be protected by emphasizing to them that the quality of their medical care will not be adversely affected if they decline to participate in this study.

800

